1 OVERVIEW OF THE STUDY

1.1 Study Design

The study design schematic is presented in [Figure 1](#).

Figure 1: Study Design Schematic

This is a randomized, double-blind, placebo-controlled, parallel-group study to evaluate the efficacy and safety of intravenously (IV) administered BIIB092 in participants with progressive supranuclear palsy (PSP) with an open-label extension.

Overall study design: The study design schematic is presented in [Figure 1](#). The study will consist of a 52-week double-blind treatment period, which will be followed by a long-term open label extension period for follow up. Participants will be randomized to receive BIIB092 or placebo. Approximately 459 participants in total will be randomized in a 2:1 ratio to receive BIIB092 or placebo (306 participants active or 153 placebo). In the double-blind treatment period of the study, participants will be dosed approximately once every 4 weeks (Q4W) for approximately 48 weeks (up to a total of 13 times). At Week 52, participants completing the double-blind treatment period may choose to continue into the open-label extension period of this study, in which, all participants will receive BIIB092. Participants will be dosed approximately once- every 4 weeks throughout the duration of the open-label extension period. The duration of the open-label extension will vary depending on the date of enrollment of the participant in the study. The study is expected to continue until BIIB092 is commercially available, the development program is terminated, or the study is terminated at the discretion of the sponsor, whichever comes first.

Study visits: Study visits will be conducted approximately every 4 weeks. Study drug will be administered and safety, efficacy, and other assessments will be performed. The study will generally be conducted on an outpatient basis unless some procedures would be better performed on an inpatient basis based on the needs of the participant. Participants will be observed and monitored by study personnel for approximately 2 hours after the end of an infusion. Participants with ongoing AEs or serious AEs (SAEs) will remain at the site or be sent to an inpatient monitoring facility until the Investigator has determined that these events have resolved or do not require inpatient monitoring.

Study assessments:

- Participants will be closely monitored for safety throughout the study. Physical examinations, vital sign measurements, 12-lead electrocardiograms (ECG), and clinical laboratory evaluations, including assessments for anti-drug antibody (ADA) will be performed. AEs will be closely monitored. [REDACTED]
[REDACTED]
- PSP related signs, symptoms and quality of life will be assessed using clinical assessments: PSP Rating Scale (PSPRS), Movement Disorder Society-sponsored revision of the Unified Parkinson's Disease Rating Scale (MDS-UPDRS Part II), Schwab and England Activities of Daily Living (SEADL) scale, Clinical Global Impression of Severity (CGI-S), Clinical Global Impression of Change (CGI-C), Montreal Cognitive Assessment (MoCA), [REDACTED]
[REDACTED] and PSP Quality of Life scale (PSP-QoL) and neuropsychological testing (RBANS, phonemic fluency, letter-number sequencing, and color trails test).
- Caregiver burden will also be assessed [REDACTED]
[REDACTED].
- Blood will be collected for ADA (as part of the assessment for immunogenicity) PK, PD, and exploratory biomarker analysis from each participant during this study in the double-blind period and in the open-label extension period.
- Structural changes in brain regions associated with PSP disease progression will be assessed using MRI. It is anticipated that each participant will have total of 4 MRIs over the course of the study, including an MRI during the screening period (up to Day - 14) and at Weeks 24, 52, and 100.
- [REDACTED]
[REDACTED]
[REDACTED]
[REDACTED]
[REDACTED]
[REDACTED]
[REDACTED]
[REDACTED]
- Participants in the QMA substudy will undergo quantitative assessments of core motor features of PSP using wearable sensors to measure gait, postural instability, motor function, and falls.

Home visits: After Week 24, except for those visits when clinical scales, LPs, or MRI assessments are performed, visits and procedures may be performed in the home as long as appropriate services are available to perform the required study procedures and adequately monitor for potential safety events. In the double-blind period of the study, Weeks 28, 32, 40, and 44 may qualify for home visits.

In the open-label extension period of the study, Week 68, 72, 80, 84, 92, 96, 104, 108, 116, 120, 128, 132, 140, 144, 152, 156, 164, 168, 176, 180, 188, and 192 visits may qualify for a home visit. However, in the event that the participant experiences a clinically significant infusion reaction as determined by investigators during the first 24 weeks of the protocol, the participant should not be administered BIIB092 in the home unless previously approved by the Study Investigator.

Discontinuation of Study treatment and/or Study Withdrawal: Participants who discontinue study treatment may belong to 1 of the following groups:

- Participants who discontinue study treatment but remain enrolled until the end of the study
- Participants who discontinue study treatment and later withdraw from the study
- Participants who discontinue study treatment and immediately withdraw from the study

Participants who discontinue study treatment during the double-blind period of the study (prior to Week 52) and remain enrolled in the study will be expected to complete the scheduled safety and efficacy evaluations until the end of the study or until the decision is made to withdraw from the study (see **Error! Reference source not found.** for schedule of evaluations in the Protocol).

AEs/SAE collection will be up to 30 days after the last dose of study treatment and will continue for as long as the participant remains enrolled in the study.

Early discontinuation visit procedures should be completed for any participant who discontinues study treatment and also withdraws from the study at any time prior to end of study. All SAEs that occur until 30 days after last dose of study treatment should be monitored and/or recorded. In the double-blind period, participants who withdraw from the study should be encouraged to return to the clinic at Week 52 to complete the Week 52 procedures. Further details on the schedule of assessment is contained in Section 2 of the protocol.

1.2 Number of Participants

It is anticipated that approximately 459 male and female participants will be dosed in this study. Approximately 459 participants will be randomly assigned, in 2:1 ratio, to receive 2000 mg of BIIB092 or placebo (306 participants active and 153 placebo) administered by IV approximately once Q4W. Randomization is stratified by country and screening Color Trails Test (CTT) Part 2 completion time of either ≤ 170 or > 170 seconds. Anticipating a dropout rate of approximately 25%, approximately 345 participants (230 participants in the BIIB092 treatment group and 115 participants in the placebo group) are expected to complete the study through Week 52.

1.3 Start of Study and End of Study Definitions

The date the first participant signs a study-specific informed consent form will be defined as the start of the study. A participant is considered enrolled when the study-specific informed consent form is signed. The date that the last participant completes the last study visit or scheduled procedure will be defined as the end of the study.

1.4 Treatment

Study treatment is defined as any investigational treatment(s), marketed product(s), placebo or medical device intended to be administered to a study participant according to the study randomization or treatment allocation

| Study Treatment | Unit dose strength(s)/Dosage level(s) | Dosage formulation Frequency of Administration | Route of Administration |
|------------------------|---|---|--------------------------------|
| BIIB092 | 2000 mg | Once every 4 weeks (Q4W) | IV |
| Placebo | Matching dose volume 0.9% NaCl or 5% Dextrose | Once every 4 weeks (Q4W) | IV |

All participants are centrally randomized using an Interactive Response Technology (IRT). Before the study is initiated, each user receives log in information and directions on how to access the IRT. Randomization is stratified by country and screening CTT Part 2 completion time of either ≤ 170 or > 170 seconds.

2 DESCRIPTION OF OBJECTIVES AND ENDPOINTS

The objectives and endpoints from the protocol Section 4 are described below.

| Objective | Endpoint |
|---|--|
| Primary | |
| To evaluate the efficacy of BIIB092, compared to placebo, as measured by a change from baseline in the PSP Rating Scale (PSPRS) at Week 52. | The primary efficacy endpoint will be evaluated by comparing the change from baseline in the total PSPRS score at Week 52 in participants treated with BIIB092 relative to the change from baseline in the total PSPRS score in participants treated with placebo. |
| To assess the safety and tolerability of BIIB092, relative to placebo, by measuring the frequency of deaths, SAEs, and AEs leading to discontinuation, and Grade 3 & 4 laboratory abnormalities. | The primary safety endpoint will be evaluated by tabulating the numbers and percentages of deaths and unique participants with SAEs and AEs leading to discontinuation, and Grade 3 & 4 laboratory abnormalities. |
| Key Secondary | |
| To evaluate the efficacy of BIIB092, compared to placebo, as measured by a change from baseline in the Movement Disorder Society-sponsored revision of the Unified Parkinson's Disease Rating Scale (MDS-UPDRS) Part II at Week 52. | The impact of BIIB092 on the MDS-UPDRS Part II will be evaluated relative to the change from baseline at Week 52 in the BIIB092-treated participants and compared to that of the placebo-treated participants. |
| To evaluate the efficacy of BIIB092, compared to placebo, as measured by the Clinical Global Impression of Change (CGI-C) at Week 52. | The impact of BIIB092 on the CGI-C scale score will be evaluated at Week 52 in the BIIB092-treated participants and compared to that of the placebo-treated participants. |

| | |
|--|--|
| 
To evaluate the efficacy of BIIB092, compared to placebo, as measured by a change from baseline in the Repeatable Battery for the Assessment of Neuropsychological Disease Severity (RBANS) at Week 52.
 | 
The impact of BIIB092 on the RBANS scale will be evaluated relative to the change from baseline at Week 52 in the BIIB092-treated participants and compared to that of the placebo-treated participants.
 |
| 
To assess the impact of BIIB092 on quality of life, relative to placebo, as measured by change from baseline on the Progressive Supranuclear Palsy Quality of Life scale (PSP-QoL) at Week 52.
 | 
The impact of BIIB092 on the PSP-QoL will be evaluated relative to the change from baseline at Week 52 in the BIIB092-treated participants and compared to that of the placebo-treated participants.
 |
| 
Other Secondary
 | |
| 
To assess the efficacy of BIIB092, relative to placebo, as measured by a change from baseline at Week 48 (Week 52 for Clinical Global Impression of Severity [CGI-S]) on the following instruments:
 
 • Schwab and England Activities of Daily Living (SEADL) Scale • CGI-S • Phonemic Fluency Test • Letter-Number Sequencing Test (LNS) • Color Trails Test • Montreal Cognitive Assessment (MoCA) | 
The impact of BIIB092 on the following instruments:
 
 • SEADL Scale • CGI-S • Phonemic Fluency Test • LNS Test • CTT • MoCA 
will be evaluated relative to the change from baseline at Week 48 (Week 52 for CGI-S) in the BIIB092-treated participants and compared to that of the placebo-treated participants.
 |
| 
To assess the immunogenicity of BIIB092.
 | 
Immunogenicity of BIIB092 will be measured by assessment of the presence or absence of anti-BIIB092 antibodies (anti-BIIB092) in serum.
 |
| 
To assess the efficacy of BIIB092, relative to placebo, as measured by absolute and percent change from baseline of brain volumes, as determined by magnetic resonance imaging (MRI), at Week 52 in the following regions:
 
 • Ventricles • Whole brain • Midbrain • Superior cerebellar peduncle • Third ventricle | 
The impact of BIIB092 on brain volumes, as determined by MRI in the following regions:
 
 • Ventricles • Whole brain • Midbrain • Superior cerebellar peduncle • Third ventricle • Frontal lobe • Pons |

| | |
|---|---|
| 
• Frontal lobe• Pons | will be evaluated relative to the absolute and percent changes from baseline at Week 52 in the BIIB092-treated participants and compared to that of the placebo-treated participants. |
| Tertiary/Exploratory | |
| 
[Redacted text]
 
• [Redacted text]• [Redacted text]• [Redacted text] 
[Redacted text]
 
• [Redacted text]• [Redacted text] 
[Redacted text]
 
[Redacted text]
 | 
[Redacted text]
 
• [Redacted text]• [Redacted text]• [Redacted text] 
[Redacted text]
 
[Redacted text]
 
• [Redacted text]• [Redacted text] 
[Redacted text]
 
[Redacted text]
 
[Redacted text]
 
[Redacted text]
 
[Redacted text]
 
[Redacted text]
 
[Redacted text]
 |

| | |
|---|---|
| 
[REDACTED]
 
[REDACTED]
 
[REDACTED]
 
[REDACTED]
 
[REDACTED]
 | 
[REDACTED]
 
[REDACTED]
 
 • [REDACTED] • [REDACTED] 
[REDACTED]
 
[REDACTED]
 
 • [REDACTED] • [REDACTED] 
[REDACTED]
 
[REDACTED]
 
[REDACTED]
 |
| 
Open-Label Extension Phase
 | |
| 
To assess the long-term safety and tolerability of BIIB092 in participants with PSP.
 | 
The tertiary endpoint will be incidence of AEs, SAEs, and death.
 |
| 
To assess the long-term efficacy of BIIB092 in participants with PSP.
 | 
The tertiary endpoints will be change from baseline over the placebo-controlled period and long-term extension period for clinical and health-outcomes assessments.
 
This study includes an optional substudy to measure quantitative movement assessments (QMAs) using wearable sensors. The QMAs will measure gait, postural instability, motor function, and falls in a subset of participants participating in the long-term extension period.
 |

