The impact of BIIB092 on brain volumes, as determined by MRI in the regions mentioned above, will be evaluated relative to the change from baseline at Week 52 in the BIIB092-treated participants to that of the placebo-treated participants.

Tertiary objectives and endpoints are listed in Section 4.

Extension Objective(s) The primary objective of the open-label extension period is to assess the long-term safety and tolerability of BIIB092 in participants with PSP based on the numbers and percentages of deaths and of participants with SAEs and AEs. The secondary objective is to assess the long-term efficacy of BIIB092 in these participants based on clinical and health-outcomes measures.

Study Design: Randomized, double-blind, placebo-controlled, parallel-group study with an open-label extension period.

This study includes an optional substudy to measure quantitative movement assessments (QMAs) using wearable sensors. The QMAs will measure gait, postural instability, motor function, and falls in a subset of study participants participating in the long-term extension period.

Study Location: Approximately 98 sites are planned globally.

CONFIDENTIAL

The information contained herein may not be used, disclosed, or published without the written consent of Biogen MA Inc.

Number of Planned Participants: Approximately 459 participants will be randomly assigned, in a 2:1 ratio, to receive BIIB092 or placebo (306 participants in the BIIB092 treatment group and 153 in the placebo group).

Anticipating a dropout rate of approximately 25% (based on previous clinical studies in participants with PSP), approximately 345 participants (230 participants in the BIIB092 treatment group and 115 participants in the placebo group) are expected to complete the study through Week 52. Using a two-sided, two-sample t-test, with an alpha level set at 0.05, this sample size will provide 80% power to detect a difference of 3.2 points in the change in PSPRS total score from baseline to Week 52 for BIIB092 relative to placebo, assuming a common standard deviation of 9.95 in the change in PSPRS total score from baseline to Week 52.

Study Population: This study will be conducted in male and female participants with probable or possible PSP.

Women of childbearing potential (WOCBP) and sexually active fertile men with partners who are WOCBP must use highly effective birth control in Study 251PP301.

Detailed criteria are described in Section 6.

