17.4.2. Safety Analyses

Safety analyses will be performed by as-treated treatment group for treated participants. Safety endpoints include the frequency and proportion of participants with AEs, SAEs, AEs leading to discontinuations and deaths, and other significant AEs reported on case report forms. Other safety endpoints include laboratory abnormalities, changes in laboratory parameters, changes in vital signs, physical findings, and ECGs.

In general, AE presentations will be by system organ class and preferred term.

The primary safety analyses will be for comparative safety of BIIB092 to placebo in the double-blind treatment period. Safety endpoints will include data up to the start of the open-label extension period for participants who completed the double-blind treatment period and continue into the open-label extension, or up to last dosing date plus 30 days for participants discontinuing study treatment during the double-blind treatment period.

Additional safety analyses will include all events reported through the time of database lock for the cumulative BIIB092-treated participants. Safety endpoints will include data from the first dose of BIIB092 in the study up to the last dose of BIIB092 treatment in the study plus 30 days.

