3.2 Analysis Period

Depending on the purpose, different analyses will be conducted on the following study periods:

1. **OLE period**. Only data in the OLE period will be included in these analyses. This OLE analysis period will be applied to all the AE analyses, and the analyses will include all subjects who were dosed in the OLE period.
2. **Placebo-controlled and OLE period**. All the data in the placebo-controlled and OLE periods will be included in these analyses. This analysis period will be applied to all efficacy analyses. The analyses will include all subjects who were dosed in the study including those who did not enroll into the OLE period.
3. **Active treatment (placebo-controlled and OLE) period**. The active treatment period is defined as the study period(s) in which a subject received BIIB092. For early start subjects, all data from placebo-controlled and OLE periods will be included. For late start subjects,

only data in the OLE period will be included. This analysis period will be applied to all safety analyses, and the analyses will include all subjects who were dosed in the study except for subjects who received only placebo in the placebo-controlled period and did not get dosed in the OLE period.

For a given output, both the analysis population and the analysis period will determine which subjects will be included. For example, the incidence table of adverse events in the OLE period will include subjects in the safety population for the OLE period, i.e., all randomized subjects who received at least one dose of study treatment in the OLE period. The incidence rate table of adverse events in the active treatment (placebo-controlled and OLE) period will include subjects in the safety population for the active treatment period, i.e., all randomized subjects who received at least one dose of treatment in the active treatment period. In this SAP we do not separately define the analysis population in each analysis period.

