6.2.2 Summary and incidence analysis

Overall summary of AE table will be done for the OLE period, as well as for the active treatment (placebo-controlled and OLE) period presented by OLE treatment group. The following information will be summarized: the number of subjects with any AE, with any AE by maximum severity (as assessed by the investigator), the number of subjects with any related AE (related to study drug as assessed by investigator), the number of subjects with SAE, the number of subjects with related SAE, the number of subjects with AE leading to study drug discontinuation, the number of subjects with an AE that led to withdrawal from the study and the number of subjects with a fatal event.

The sorting order for AE incidence tables, unless otherwise specified, will be by decreasing frequency order of “BIIB092 total” column within each category in the tables presented by OLE treatment group. A subject is counted only once within each category in each table. For example, for the table of AEs by system organ class and preferred terms sorted by decreasing frequency presented by treatment group, system organ class will be presented in decreasing frequency order of BIIB092 total column, and within each system organ class, preferred terms will be presented in decreasing frequency order of BIIB092 total column. A subject is counted only once within each system organ class and preferred term.

The following AE incidence proportion tables will be provided for the OLE period (presented by the OLE treatment group unless otherwise specified):

1. AEs by system organ class and preferred term sorted by decreasing frequency
2. AEs by system organ class and preferred term sorted by alphabetical order
3. AEs by system organ class, high level group term and preferred term
4. AEs by system organ class
5. AEs by preferred term
6. AEs with an incidence of 2% or more in any treatment group by preferred term
7. AEs with an incidence of 5% or more in any treatment group by preferred term
8. Severe or very severe AEs by system organ class and preferred term
9. Severe or very severe AEs by preferred term

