6.2.3 Incidence rate analysis

Due to the different length of active treatment (placebo-controlled and OLE) period in early start versus late start subjects, FAIR (defined in Section 6.1) tables will be used for following AE analyses for the active treatment (placebo-controlled and OLE) period (presented by OLE treatment group):

1. AEs by system organ class and preferred term sorted by decreasing frequency
2. AEs by system organ class, high level group term and preferred term
3. AEs by preferred term
4. Severe or very severe AEs by system organ class and preferred term
5. Severe or very severe AEs by preferred term
6. Related AEs by system organ class and preferred term
7. SAEs by system organ class and preferred term
8. SAEs by preferred term
9. Related SAEs by system organ class and preferred term

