6.3.2 Qualitative analyses

For all qualitative analyses, all values will be included (not just the “analyzed record” within each visit window in the quantitative analyses).

Shift analyses

Laboratory data will be summarized using shift tables where appropriate. Each subject’s hematology, blood chemistry, coagulation and urinalysis (excluding microscopic examination) values will be flagged as “low”, “normal”, or “high” relative to the normal ranges of the central laboratory or as “unknown” if no result is available. Each subject’s urinalysis values for protein, glucose, blood, and leukocyte esterase will be flagged as “abnormal” if positive, “normal” if negative, or “unknown” if no value is available.

For each parameter, the analysis will be based on subjects with at least one post-baseline value. Shifts from baseline to high/low status will be presented for hematology, blood chemistry, coagulation and urinalysis (specific gravity and pH), and shifts from baseline to abnormal (or unknown to abnormal) will be presented for urinalysis parameters (protein, glucose, blood, and leukocyte esterase). Shift to low includes normal to low, high to low, and unknown to low; shift to high includes normal to high, low to high, and unknown to high. Subjects need to have at least one post-baseline evaluation and a baseline value either unknown or not low/high/abnormal in order to be included in the analysis.

Grade analyses

Each scheduled laboratory parameter will be summarized both by worst post-baseline grade and by worst cumulative post-baseline grade; this analysis includes the primary endpoints of Grade 3 and 4 laboratory abnormalities. Subjects need to have at least one post-baseline evaluation in order to be included in the analysis. Common Terminology Criteria for Adverse Events v4.0.3 (CTCAE) published on 14 June 2010 will be used for grade determination. Grade determination is based solely on laboratory values and does not take other clinical information into account; therefore, a lower grade may be assigned to a laboratory parameter result since clinical information does not contribute to the grading assessment. Thus, the incidence of higher grades may be underestimated.

For calcium (mmol/L), the laboratory result will be corrected by the concurrent albumin (g/L) result for CTCAE grade determination. The derivation of the corrected calcium (mmol/L) will be derived as follows:

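### OLE SAP 6.2.3 leaves fatal SAEs, and AEs leading to discontinuation or withdrawal, out of its follow-up-adjusted rates over the active-treatment period

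*SAP*

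**What the plan says.** - **Endpoint.** OLE SAP section 2, extension rows: "The tertiary endpoint will be incidence of AEs, SAEs, and death".
- **Cumulative analysis.** Protocol 17.4.2: "Additional safety analyses will include all events reported through the time of database lock for the cumulative BIIB092-treated participants".
- **Windows.** OLE SAP 3.2 (Analysis Period), on the active-treatment period: "For early start subjects, all data from placebo-controlled and OLE periods will be included". Late-start subjects contribute extension data only. Placebo subjects never dosed in the extension are left out.
- **Reason for rates.** OLE SAP 6.2.3 opens with "Due to the different length of active treatment (placebo-controlled and OLE) period in early start versus late start subjects" and then lists nine FAIR tables. They cover all AEs, severe or very severe AEs, related AEs, SAEs and related SAEs.
- **Other rates over the same period.** Sections 6.2.4 and 6.2.5 add exposure-adjusted rates for potential immune/hypersensitivity reactions and for infusion reactions.
- **Deaths, discontinuations and withdrawals over the active-treatment period.** The overall summary in 6.2.2, by start group, gives the number of subjects with an AE leading to discontinuation, and then "the number of subjects with an AE that led to withdrawal from the study and the number of subjects with a fatal event". No rate is attached.
- **The same events in the extension alone.** Items 16 to 18 of 6.2.2 are incidence-proportion tables for the OLE period only.

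**The concern.** The SAP gives a reason for using rates and then does not apply it to the gravest outcome. Of the three components of the extension endpoint, AEs and SAEs have rates over BIIB092 exposure and death does not. AEs that stop treatment or lead to withdrawal are in the same position.

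Early-start subjects bring up to 52 more weeks at risk into the active-treatment columns than late-start subjects. Crude figures therefore differ between the columns even if the drug has no effect on mortality, and they differ in the direction that makes longer treatment look worse. The OLE-period tables avoid this because both groups are observed over the same window. They cannot replace a cumulative rate, because they exclude what happened to early-start subjects in their first 52 weeks on BIIB092.

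**Working it through.** **Inputs from the documents.** Allocation is 306 to 153 and dropout to Week 52 is 25% (OLE SAP 1.2). The windows are those of OLE SAP 3.2. OLE SAP 5.3 says too few subjects will have reached Week 100 at the interim lock. Week 100 is 100 − 52 = 48 weeks of extension, so a mean below 48 weeks is plausible, but no mean is stated.

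**Assumptions.** All Week 52 completers enter the extension and each is followed for w weeks there. Dropout is spread evenly over the placebo-controlled year and ends follow-up. The death hazard is constant and equal in both groups.

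**The plan's own figure.** Completers: 459 × 0.75 = 344.25 (229.5 and 114.75), which reproduces the stated 345 (230 and 115). About 115 late-start subjects could therefore enter the active-treatment analysis, against all 306 early-start subjects dosed.

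**Ratio of crude percentages, early to late, for rare events.**

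- Without dropout: (52 + w) / w.
- With 25% dropout, mean placebo-controlled time is 0.75 × 52 + 0.25 × 26 = 45.5 weeks. The ratio is (45.5 + 0.75w) / w.

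The last column replaces the rare-event approximation by 1 − exp(−hazard × time), for hazards of 5 to 20 deaths per 100 subject-years.

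| w (weeks) | No dropout | 25% dropout | 25% dropout, hazard 0.05 to 0.20 |
|---|---|---|---|
| 12 | 64/12 = 5.33 | 54.5/12 = 4.54 | 4.44 to 4.15 |
| 24 | 76/24 = 3.17 | 63.5/24 = 2.65 | 2.59 to 2.42 |
| 36 | 88/36 = 2.44 | 72.5/36 = 2.01 | 1.97 to 1.85 |
| 48 | 100/48 = 2.08 | 81.5/48 = 1.70 | 1.66 to 1.56 |

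**One case in full: hazard 0.10 per year, w = 24, 25% dropout.**

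- Late: 1 − exp(−0.10 × 24/52) = 4.5%.
- Early completers: 1 − exp(−0.10 × 76/52) = 13.6%.
- Early dropouts, averaged over the year: 1 − (1 − exp(−0.10))/0.10 = 4.8%.
- Early overall: 0.75 × 13.6% + 0.25 × 4.8% = 11.4%.
- Ratio: 11.4 / 4.5 = 2.5.

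**The same case as a rate.** Expected deaths are 34.9 of 306 and 5.19 of 115. Subject-years to the planned end of follow-up are 306 × (0.875 + 0.75 × 24/52) = 373.7 and 115 × 24/52 = 53.1. The rates are 9.3 and 9.8 per 100 subject-years, a ratio of 0.96. If follow-up stops at death, as the last day on study implies, both expected rates equal the assumed 10 and the ratio is 1.0.

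**The case against.** **The protocol asks for percentages.** Its synopsis sets the extension objective "based on the numbers and percentages of deaths and of participants with SAEs and AEs", and 17.4.2 speaks of frequency and proportion. The crude summary meets that text, so no protocol commitment is broken. But the wording covers AEs, SAEs and deaths alike, and the SAP still adds rates for AEs and SAEs.

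**The information is not lost.** A reader might infer that mortality on BIIB092 cannot be judged from the planned outputs. The documents do not support that. Every FAIR table within a group shares the denominator defined in 6.1.4, so a rate can be worked out from the count. Deaths are reported as SAEs (Protocol 10.14) and sit inside the SAE rates. Items 16 to 18 compare like windows. The placebo-controlled SAP tabulates fatal SAEs against placebo. This limits the seriousness of the point. It does not explain why the planned active-treatment display of deaths is the unadjusted one.

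**A rate need not return exactly 1.0.** PSP is progressive, and late-start time begins a year later, among those still in the study. With a rising hazard, FAIR would not be fully comparable either. It would still remove the difference in follow-up length, which is the SAP's own reason for using it.

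**Laboratory grades.** A reader might also infer that the extension drops a required Grade 3/4 analysis, since the primary safety endpoint involves "tabulating the numbers and percentages of deaths and unique participants with SAEs and AEs leading to discontinuation, and Grade 3 & 4 laboratory abnormalities". That endpoint is relative to placebo, and the placebo-controlled SAP covers it in 6.3.2: "this analysis includes the primary endpoints of Grade 3 and 4 laboratory abnormalities". The extension endpoint does not include grades. OLE SAP 6.3.1 still gives by-visit minima and maxima for chemistry and coagulation.

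**Conclusion.** The point holds as an inconsistency within the OLE SAP. Section 6.2.3 gives unequal active treatment as the reason for rates, yet fatal SAEs and AEs leading to discontinuation or withdrawal receive none over that period.

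At equal mortality the crude percentage in early start would be about 1.6 to 4.5 times that in late start, for mean extension follow-up of 48 down to 12 weeks with 25% dropout, and up to about 5 times without dropout. A reader might take a single multiple, such as two to three, as a property of the plan. It is not: the size depends on extension follow-up, dropout and hazard. Only the 25% dropout comes from the documents. With much longer follow-up the distortion shrinks, to about 1.2 (rare events, with dropout) at 104 weeks: (45.5 + 78)/104.

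The distortion is confined to the active-treatment overall summary. The extension-only tables are not affected, and no formal test of deaths is planned. This is a low-cost improvement to the reporting, not a flaw that undermines the safety analysis.

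**What to change.** In OLE SAP 6.2.3, add three FAIR tables for the active-treatment period, by early start, late start and total: fatal SAEs, AEs leading to discontinuation of study treatment, and AEs leading to withdrawal from the study. In 6.2.2, show the same three rates beside the counts in the active-treatment overall summary. Keep the counts, the percentages and the OLE-period tables as they are.

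The cost is a few lines of SAP text and three more runs of a calculation already planned for the other tables. The FAIR denominator is defined in 6.1.4, the events are already collected, and no new data are needed.
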